We recently found, in an observational study, that patients resuscitated with the diluted 5% albumin solution received five times more volume compared to patients resuscitated with the concentrated 20% albumin solution [11]. Despite this difference, a trend towards higher mean arterial blood pressure up to four hours after a bolus of 20% albumin (compared to a bolus of 5% albumin) was seen (P = 0.056, Figure 1). In addition, more patients receiving 5% albumin needed further fluid boluses within 24 hours as compared to patients receiving 20% albumin (58% versus 45%, P = 0.049). Finally, patients resuscitated with concentrated 20% albumin received approximately 30 times less chloride than those in the 5% albumin group. This is an important SWIPE Protocol UK V2.2, dated 18^{th} May 2016 EudraCT No: 2016-001940, UK Protocol ID: R04336

finding since administration of chloride-rich solutions is associated with more complications, including severe renal failure requiring dialysis [12, 13].

Figure 1. Mean arterial blood pressure over the first four hours following a fluid bolus of either 100 mL, 20% albumin solution or 500 mL, 5% albumin solution, including baseline values at 0 hours.

Aims

The aim of this study is to establish the feasibility, safety, biochemical and physiological efficacy of 20% albumin compared with 5% albumin for fluid bolus therapy in critically ill patients.

Specifically, we aim to study the effect of intravenous 20% albumin infusion compared to 5% albumin infusion on the following variables:

- Mean arterial blood pressure (first 4 hours)
- Central venous pressure (first 4 hours)
- Cardiac output (first 4 hours)
- Urinary output (first 4 hours)
- Serum biochemistry (first 4 hours)

- Volume of fluid administered over the first 4 hours and first 48 ICU hours following recruitment
- Use of vasoactive medications over the first 48 ICU hours following recruitment
- Serum chloride levels over the first 48 ICU hours following recruitment
- Serum albumin levels over the first 48 ICU hours following recruitment
- Renal function based on changes in serum creatinine and urine output in the first 48 ICU hours.
- Lung function based on arterial partial oxygen pressure (PaO₂)/fraction of inspired oxygen (FiO₂) ratio in the first 48 hours in ICU

Hypotheses

- We hypothesise that the administration of 20% albumin for fluid resuscitation in critically ill patients will be feasible and safe when compared to administration of 5% albumin

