- Presence of one or more of the following physiological states: systolic BP <90 mmHg, or MAP <65 mmHg, or increasing need for vasopressor drug infusion or pulse pressure variation >12 % or stroke volume variation >12%, or Cardiac index <2.2 L/min/m² or heart rate >100 or urinary output <20 ml/hr or either rising lactate levels or lactate levels >2 mmol/L or capillary refill time >3 seconds or central venous pressure <8 mmHg.

Exclusion criteria

- Confirmed or suspected pregnancy
- Patients with traumatic brain injury
- Active bleeding
- Haemoglobin level <70 g/L

• People who refuse blood products SWIPE Protocol UK V2.2, dated 18th May 2016 EudraCT No: 2016-001940, UK Protocol ID: R04336 • Patients in whom death is considered imminent (within 24 hours)

Sample size estimate

Given that in the first 48 hours the 5% albumin administered in the SAFE study [14] was a total of 1785ml (SD of 1865), we will aim to detect a decrease in fluid given to 1300ml (SD of 1368: proportionately the same as that seen in SAFE for a mean inout of 1785ml). This decrease of around 500ml in fluid input is considered of potential clinical value. To have a 90% power of detecting such a difference at an alpha level of 0.05, 195 patients will need to be randomised to each group. We have rounded this number up to 200 in each group to account for possible data loss.

Randomisation procedure

- Computer generated sets of random allocations will be produced by the Research Co-ordinator in advance of the study.
- Randomization will be by means of sealed envelopes with permuted blocks of variable size.
- Each envelope will contain a study arm allocation as well as a copy of a simplified version of the study protocol.
- Every patient who participates in any study related procedure will be assigned a unique patient number.

Intervention description

Patients will be randomised one of two arms:

• The treatment arm will receive an intravenous infusion of 20% albumin (Alburex

20®, CSL Behring, Marburg, Germany) every time the treating clinician decides SWIPE Protocol UK V2.2, dated 18th May 2016 EudraCT No: 2016-001940, UK Protocol ID: R04336 that a fluid bolus needs to be given during the first 48 hours in ICU. The treating clinician determines the volume and infusion rate of each fluid bolus.

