- Reason for admission to intensive care (post-operative complication, sepsis, medical emergency, post-operative management, other) and urgency (planned, unplanned, emergency). If surgical, date and type of operation.
- Weight and height on admission, to be used for calculation of body surface area.

Clinical Data

- Haemodynamic data: HR, ABP, CVP will be measured hourly during the study period.
- Blood gas results: PaO₂, lactate concentration, pH/H+ concentration, bicarbonate concentration, sodium concentration, chloride concentration, creatinine concentration, haemoglobin concentration and base deficit/excess will be measured hourly during the study period.
- Fluid balance Resuscitation fluids. Each fluid bolus will be recorded (type of resuscitation fluid, volume, infusion speed).

• Fluid balance – for each day or part there of. SWIPE Protocol UK V2.2, dated 18th May 2016 EudraCT No: 2016-001940, UK Protocol ID: R04336

- Baseline serum creatinine and urea pre-admission to ICU if available. Defined as
 a serum creatinine and urea taken in the six months pre-admission to hospital for
 this ICU event.
- Serum creatinine on admission, as indicated above, and as indicated clinically.
- Serum albumin on admission and as indicated clinically.
- Doses of furosemide administered (or rate of furosemide infusion).
- Doses of vasopressors and inotropes administered (or infusion rates).
- All other biochemical and haematological indices recorded as clinically indicated during the patient admission.

Outcome Data

- Primary efficacy outcome
 - Amount of resuscitation fluid (mL) administered over the first 48 hours in ICU.
- Secondary efficacy outcomes
 - The cumulative fluid balance after 48 hours in ICU.
 - The amount of vasoactive medication given over the first 4 hours after a fluid bolus and over the first 48 hours in ICU.
 - The total amount of fluids given over the first 4 hours after a fluid bolus,
 daily and over the first 48 hours in ICU.
 - The relative change in haemodynamic variables and blood gas results over the first 4 hours after a fluid bolus.
 - The relative change between baseline and peak creatinine in the first 48

hours after randomization.

- Patient-centred efficacy outcomes
 - Need for RRT
 - Renal status at 90 days
 - Hours on mechanical ventilation
 - ICU discharge status (alive or dead)
 - ICU length of stay
 - Hospital discharge status (alive or dead)

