 - Hospital outcome (discharge destination home, another hospital, advanced care institution)
 - Hospital length of stay (date of discharge)
 - Mortality status at 90 days.
- Feasibility and safety outcomes:
 - Distribution of values for primary and secondary outcome
 - Randomized / Screened patients ratio
 - Data completion rate
 - Loss to follow-up rate
 - Recruitment rate and duration
 - Separation in amount of fluid given

Safety outcomes

- Development of side-effects
- Episodes of hypotension
- Development of kidney failure

o Adverse changes in any of the physiological efficacy measures

Data analysis

Outcomes will be compared after log transformation where appropriate. Comparisons will be made using t-test and ANOVA for repeated-measures or Wilcoxon rank-signed test and Kruskall-Wallis according to the underlying distribution for continuous data and Chi-square for categorical data. A Kaplan-Meier curve with log-rank test will be performed to further compare in-hospital mortality and rate of discharge home. Logistic regression analysis will also be performed to adjust for baseline imbalances. Analysis will be an on intention-to-treat basis.

Risks and Benefits

Albumin solutions have been used for resuscitation since the 1940s. An investigation of the safety of albumin solutions showed that between 1998 and 2000, approximately 10⁷ units of such albumin solutions were administered worldwide. Adverse effects that were directly associated with albumin were an extremely rare event during this observation period [15]. There are, however, more recent reports that the use of (20%) albumin is associated with increased mortality for patients with traumatic brain injury [6]. Accordingly, patients with traumatic brain injury will be excluded from the SWIPE study. Although albumin is prepared from pooled plasma, albumin preparations currently available are considered to be non-allergenic due to the manufacturing process.

Data handling, retention, storage and destruction

Data handling

The case report form (CRF) will be developed by the members of the investigator team as a paper CRF. All data will be collected by members of the investigator team as described in the CRFs from the source data. Information recorded in the CRF should accurately reflect the subject's medical/hospital notes and must be completed as soon as it is made available.

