agreed substantial protocol amendments, will be documented and submitted for ethical and regulatory approval prior to implementation. Annual reports will be submitted to the REC and the Competent Authority (the MHRA). The UK CI and sponsor will ensure that the REC and the MHRA are notified that the trial has finished (either as expected or prematurely) within required timeframes with summary reports to be provided as required.

Funding and insurance

For patients recruited in Australia:

Funding is provided by the Austin Hospital Special Purpose Fund (Y8016) *Anaesthesia Intensive Care Trust Fund* (AICTF) for the development and completion of this project. Top-up funding is being sought via a competitive grant application. As an investigator-initiated study performed in an Australian public hospital, indemnity insurance will be provided by the public hospital (Austin Health).

For patients recruited in the United Kingdom:

Funding is provided by CSL Behring in the form of an unrestricted grant. Central Manchester University Hospitals NHS Foundation Trust will act as the sponsor for UK patients and will provide NHS indemnity.

Trial registration

This study is registered with the Australian New Zealand Clinical Trial Registry (ACTRN12615000349549) and the European Medicines Agency (EudraCT No: 2016-001940-20). Prior to commencement in the UK, this study will be registered with the ISRCTN registry. These are public access registries. All pending trial registration numbers will be provided to the HREC when the registration is

completed.

Publication

The study will be published in the name of the of the study investigators. The chief investigator will be listed as the first author and other members of the management committee will be listed alphabetically. Funding bodies will be acknowledged in the publication.

Following completion of the study and data analysis the study results will be published in a peer-reviewed critical care journal and presented at local and national intensive care conferences. In addition, we will provide a summary of the study and its findings to the staff of the two study sites.

Study findings will not be provided to trial participants as:

1. The physiological findings will be of a pilot investigation in nature.

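### The protocol sets out to establish that 20% albumin is safe compared with 5%, but its named tests and sample size can only estimate safety, and imprecisely

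*Protocol*

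**What the plan says.** - **Aim** (Protocol, Aims): "The aim of this study is to establish the feasibility, safety, biochemical and physiological efficacy of 20% albumin". The comparator is the 5% solution.
- **First hypothesis** (Protocol, Hypotheses): giving 20% albumin "will be feasible and safe when compared to administration of 5% albumin". No acceptance limit is attached.
- **Methods** (Protocol, Data analysis): t-tests, repeated-measures ANOVA or rank methods for continuous data; "Chi-square for categorical data"; Kaplan-Meier curves with a log-rank test for in-hospital mortality and discharge home; logistic regression to adjust for baseline imbalance.
- **Size** (Protocol, Sample size estimate): 195 per group, rounded up to 200, to detect a fall in mean fluid volume from 1785 mL to 1300 mL. This is the primary outcome: "Amount of resuscitation fluid (mL) administered over the first 48 hours in ICU".
- **Outcomes** (Protocol, Outcome Data): the listed safety outcomes are side-effects, hypotension, kidney failure and adverse physiological changes. Renal replacement therapy (RRT) and 90-day mortality are listed as patient-centred efficacy outcomes. No event rate is given for any of these.

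**The concern.** Most of the other hypotheses are directional: less fluid, lower central venous pressure, a higher PaO₂/FiO₂ ratio. A test of difference suits them, because rejecting the null supports the claim. The safety hypothesis is of another kind. To say that one product is safe compared with another is to say that it carries no important excess of harm. A chi-square or log-rank test can produce evidence of harm, but failing to reject its null is not evidence that harm is absent.

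The hypothesis therefore has no stated method that could support it, and the trial was not sized with it in mind. At stake is what the final report can say about safety. The named analysis yields p-values that leave open how large an excess of harm remains compatible with the data.

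**Working it through.** **1. The protocol's own sample size.** Inputs from Sample size estimate: means 1785 and 1300 mL (difference 485), SDs 1865 and 1368, 90% power, alpha 0.05.

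n per arm = (z_α + z_β)² × (SD₁² + SD₂²) / difference²

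(1865² + 1368²) / 485² = 5,349,649 / 235,225 = 22.74

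- One-sided alpha 0.05: (1.645 + 1.282)² × 22.74 gives 195, the stated figure.
- Two-sided alpha 0.05: (1.960 + 1.282)² × 22.74 gives 239.

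The stated number is thus reproduced with a one-sided test; the protocol does not state sidedness. That is a separate matter. What counts here is that no safety quantity enters the calculation.

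**2. What 200 per arm gives for a binary safety outcome.** Control risks of 10%, 15%, 20% and 25% are assumptions.

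- Half-width of the 95% interval for the risk difference when both observed risks equal p: 1.96 × √(2p(1−p)/200). At p = 0.20 this is 1.96 × √(0.32/200) = 1.96 × 0.040 = 0.078.
- Power of a two-sided 5% test against a true 5-point excess: Φ(0.05/SE − 1.96), with SE = √[(p₀(1−p₀) + p₁(1−p₁))/200]. For 20% against 25%, SE = √[(0.16 + 0.1875)/200] = 0.0417, so power = Φ(1.20 − 1.96) = 0.22.
- Largest observed excess that chi-square still leaves non-significant, with the upper 95% limit that goes with it.

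| Assumed control risk | Half-width at equal risk (points) | Power, true 5-point excess | Power, true 10-point excess | Largest non-significant excess (points) | Its upper 95% limit (points) |
|---|---|---|---|---|---|
| 10% | 5.9 | 33% | 80% | 6.5 | 13.1 |
| 15% | 7.0 | 26% | 71% | 7.5 | 15.1 |
| 20% | 7.8 | 22% | 64% | 8.0 | 16.3 |
| 25% | 8.5 | 20% | 59% | 8.5 | 17.4 |

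**3. One row worked through.** Suppose 40/200 events on 5% albumin and 56/200 on 20% albumin, an excess of 8 points.

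- Test: pooled risk 0.24, SE = √(0.24 × 0.76 × 2/200) = 0.0427, z = 1.87, p = 0.06.
- Interval: SE = √[(0.20 × 0.80 + 0.28 × 0.72)/200] = 0.0425, so 8.0 ± 8.3 points, or −0.3 to +16.3.

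The test is non-significant, yet the data are compatible with an excess of 16 points.

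**4. What excluding harm would take.** With equal true risks, one-sided 2.5% and 80% power, n per arm = (1.96 + 0.84)² × 2p(1−p)/margin².

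- To exclude a 5-point excess: 566, 801, 1005 and 1178 per arm across the four risks.
- To exclude a 10-point excess: 142, 201, 252 and 295 per arm.

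At this power, 200 per arm is far short for 5 points at every assumed risk. For 10 points it suffices at 10% risk, is about enough at 15%, and falls short at 20% and 25%.

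**The case against.** **No rule equates non-significance with safety.** A reader might infer that a non-significant chi-square will be reported as proof of safety. The documents do not support that: no such rule is written anywhere in the protocol. The point is the narrower one that the named tests cannot support the hypothesis.

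**Chi-square is not the only method.** This is right. The log-rank test is also planned for in-hospital mortality, and logistic regression yields effect estimates to which intervals could be attached. But log-rank is again a test of difference, and the regression is there to adjust for imbalance. Neither comes with a criterion for safety.

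**Safety is not confirmatory.** This also stands. The primary outcome is fluid volume, and safety is grouped with recruitment and data completion. A trial of this type needs no non-inferiority margin for such outcomes. It is a reason to scale the claim down, since the aim and first hypothesis are worded more strongly than that standing allows.

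**Intervals may be in an analysis plan that is not shown.** They may, and their absence from the protocol would not by itself be a finding. The wording of the aim and hypothesis, however, is fixed in the protocol, and so is the choice of chi-square.

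**Two arguments to leave aside.** Under Publication the protocol says "The physiological findings will be of a pilot investigation in nature", but that covers the physiological findings only and does not describe the safety data. The absence of an independent monitoring committee concerns accruing data and has no bearing on how a final comparison is interpreted.

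**Conclusion.** The point holds in limited form. The protocol states a comparative safety hypothesis, names methods that cannot support it, gives no criterion for it, and is sized on another outcome. At 200 per arm and assumed control risks of 10% to 25%, identical observed rates would still leave an excess of about 6 to 8.5 points inside the 95% interval. A true 5-point excess would be missed about 67% to 80% of the time. These figures rest on assumed risks, but a 5-point excess would usually be missed anywhere in the range.

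This does not show that the design is unsound, that a margin is required, or that the investigators intend to claim safety from a non-significant result. RRT and 90-day death come into it only if they are used to speak to safety, since the protocol lists them elsewhere. It is an inexpensive improvement to what the trial can properly say.

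**What to change.** - **Aims and Hypotheses:** replace establishing safety, and the prediction that 20% albumin will be safe, with describing or estimating the safety of 20% versus 5% albumin.
- **Data analysis:** for side-effects, hypotension and kidney failure, and for RRT and 90-day death when they are used to speak to safety, make the between-arm risk difference with its 95% confidence interval the reported result in place of the chi-square p-value.
- **Interpretation:** add a sentence that a non-significant difference will not be reported as evidence of safety.

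The cost is a few sentences in three sections and a more modest safety claim. No margin, redesign, new data or additional patients are needed.

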- We hypothesise that a lower volume of resuscitation fluid will be administered over the first 4 and 48 hours in ICU in patients receiving 20% albumin than in patients receiving 5% albumin.
- We hypothesise that the cumulative fluid balance over the first 48 hours in ICU will be significantly lower in patients receiving 20% albumin than in patients receiving 5% albumin.
- We hypothesise that the administration of 20% albumin will create a significantly greater increase in the hourly and mean arterial blood pressures over the study period compared to the 5% albumin.

- We hypothesise that the mean central venous pressure will be significantly lower in patients receiving 20% albumin than in those patients receiving 5% albumin.
- We hypothesise that patients receiving 20% albumin will require less vasoactive medications over the study period as compared to patients receiving 5% albumin.
- We hypothesise that the overall administration of chloride will be less in patients receiving 20% albumin than in patients receiving 5% albumin.
- We hypothesise that 20% albumin administration will significantly reduce peak serum creatinine in the first 48 hours following randomisation when compared to 5% albumin administration.
- Finally, we hypothesise that the administration of 20% albumin will significantly increase the PaO₂/FiO₂ ratio when compared to the administration of 5% albumin.

Relevance and Importance

- The association between fluid accumulation and poor patient outcomes has been established.
- Fluid resuscitation with 20% albumin may reduce the volume of fluid administration.
- A reduced volume of fluid administered during critical illness may achieve similar hemodynamic improvements without the need for additional volume administration

Methodology

Study design

The SWIPE study is an investigator-initiated, multi-centred, open label, randomisedcontrolled trial.

Participant recruitment and selection

All patients will be recruited if they meet the inclusion criteria and no exclusion criteria.

Inclusion criteria

- Admitted to the intensive care unit at participating sites for less than 24 hours.
- Age 18 years or greater
- Need for fluid bolus as determined by the treating clinician

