The control arm will receive an intravenous infusion of 5% albumin (Alburex 5[®], CSL Behring, Marburg, Germany) every time the treating clinician decides that a fluid bolus needs to be given during the first 48 hours in ICU. The treating clinician determines the volume and infusion rate of each fluid bolus.

Randomised participants in this study will receive and infusion of 20% albumin (treatment group) or 5% albumin (control group) each time the treating physician decides that a fluid bolus needs to be given during the first 48 hours of ICU. The treating clinician determines the volume and infusion rate of each bolus. Other fluids (nutrition, drug infusions, blood products) are given as per the discretion of the treating clinician.

Blinding

Blinding in this trial is not possible as Alburex $20^{\$}$ comes in 100 mL glass bottles whereas Alburex $5^{\$}$ comes in 500 mL bottles.

Monitoring

- Routine clinical monitoring shall continue after recruitment to the study.
- Routine monitoring of critically ill patients admitted to the ICU includes:
 - Heart rate (HR)
 - Arterial blood pressure (ABP)
 - Central venous pressure (CVP)

Oxygen saturation (SpO₂)
 SWIPE Protocol UK V2.2, dated 18th May 2016
 EudraCT No: 2016-001940, UK Protocol ID: R04336

- Urine output (UO)
- Respiratory rate (RR)
- Temperature
- o Fluid intake
- Fluid output
- Ventilator settings
- Blood gas results
- Serum creatinine
- Serum albumin

Patient Care

- Participation in the study shall not affect patient treatment in any other way.
- All additional therapies shall be administered at the discretion of the treating clinician.
- These therapies include:
 - Oxygen therapy
 - Antibiotics
 - Radiological investigations
 - Surgical interventions

There will be no attempt to control any other treatment. In particular there will be no attempt to control vasopressor therapy, oxygen therapy, antibiotics, blood, blood products and surgical intervention.

Data collection

The case report form will collect the information detailed below. The electronic medical records and previous volumes of notes will be accessed to collect baseline data where appropriate. Laboratory data will be accessed to acquire the items detailed below. We will perform a data review after the first 20 patients to ensure our data capture strategy is appropriate.

Data will be collected on the following variables:

Patient data

- Code for patient, gender and age. Date of admission to ICU and to hospital.

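### The blood-pressure hypothesis runs over an undefined study period while its aim and only efficacy outcome use 4 hours, and the CVP hypothesis and outcome differ in quantity

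*Protocol*

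**What the plan says.** The Protocol describes the pressure endpoints in four places.

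- **Hypotheses, blood pressure:** 20% albumin "will create a significantly greater increase in the hourly and mean arterial blood pressures over the study period".
- **Hypotheses, CVP:** "the mean central venous pressure will be significantly lower in patients receiving 20% albumin than in those patients receiving 5% albumin". No window is given.
- **Aims:** "Mean arterial blood pressure (first 4 hours" and "Central venous pressure (first 4 hours", each in brackets after the variable. The start of the 4 hours is not stated.
- **Data collection, Outcome Data, secondary efficacy outcomes:** "The relative change in haemodynamic variables and blood gas results over the first 4 hours after a fluid bolus". This is the only efficacy outcome that covers MAP or CVP.

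Under Clinical Data, "HR, ABP, CVP will be measured hourly during the study period". Under Patient Care there is "no attempt to control vasopressor therapy". The trial is open label.

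**The concern.** A hypothesis, its aim and its outcome should describe the same measurement. For blood pressure they do not. The hypothesis is an increase over a period that appears to be 48 hours, and the outcome is a relative change over 4 hours. Nothing in the outcome list tests the hypothesis as written.

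For CVP the hypothesis is silent on the window, so the 4-hour aim and outcome could supply it. The mismatch there is in the quantity. A lower mean level is not the same claim as a smaller relative change from baseline, and the two can differ in size or direction if the arms start at different values.

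What is at stake is which analysis counts as the test. Hourly data make both a 4-hour and a longer analysis possible, treatment is known to everyone, and the Protocol does not say which one decides the hypothesis.

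**Working it through.** **1. What *study period* is likely to mean.** The term is not defined. Three places bear on it.

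- The vasoactive-drug hypothesis uses the same term, and the matching aim gives 48 ICU hours after recruitment.
- The Intervention description gives study fluid during the first 48 hours in ICU.
- Where two windows are wanted, both are written: resuscitation volume has 4 and 48 hours in the Hypotheses, and vasoactive drugs and total fluids have both in the outcome list. The haemodynamic outcome has only 4 hours.

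Forty-eight hours is therefore the natural reading, but it is an inference.

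**2. The statements side by side.**

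| | Hypothesis | Aim | Efficacy outcome |
|---|---|---|---|
| MAP, window | study period (undefined) | first 4 h, start not stated | 4 h after a fluid bolus |
| MAP, quantity | increase, hourly and mean | not stated | relative change |
| CVP, window | none | first 4 h, start not stated | 4 h after a fluid bolus |
| CVP, quantity | mean level | not stated | relative change |

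**3. Sensitivity to the window.** The Protocol gives no effect size, SD or power for MAP or CVP, so there is no figure to reproduce. What follows is an illustration.

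*From the Protocol:* 200 patients per arm; 1785 mL assumed for control and 1300 mL for treatment (Sample size estimate); bottles of 500 mL and 100 mL (Blinding).

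*Assumed:* two-sided 5% test; a 4-hour effect of 0.30 SD, confined to the 4 hours after each bolus; boluses that do not overlap; equal SD for the 4-hour and 48-hour means unless stated.

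Power ≈ Φ(d√(n/2) − 1.96) + Φ(−d√(n/2) − 1.96), with √(200/2) = 10.

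- 4-hour window: d = 0.30, d√(n/2) = 3.0, power 85%.
- Control volume in full bottles: 1785/500 = 3.57 boluses; × 4 h = 14.3 h; 14.3/48 = 30%. Then d = 0.30 × 0.298 = 0.089, power 15%. If the SD of the 48-hour mean is 0.8 or 0.6 of the 4-hour SD, power is 20% or 32%.
- Half of the hours post-bolus: d = 0.15, power 32% (up to 71% at SD ratio 0.6).
- Control volume in 250 mL boluses (assumed): 1785/250 = 7.1; × 4 h = 28.6 h; 28.6/48 = 60%. Then d ≈ 0.18, power about 43%.
- Treatment volume in 100 mL bottles: 1300/100 = 13; × 4 h = 52 h, which exceeds 48 h. The share is capped at 100%, d = 0.30, power 85%.

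The denominator is uncertain too. Patients may enter up to 24 hours after ICU admission, so if treatment stops at 48 ICU hours as little as about 24 hours may remain, and 14.3/24 = 60%.

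**4. Cost of leaving the choice open.** Suppose that a two-sided 5% result in either window could be claimed as confirmation. The type I error then depends on the correlation between the two test statistics, which is assumed here. At correlation 0 it is 1 − 0.95² = 9.75%. Simulation gave 9.7% at 0, 9.0% at 0.5, 7.8% at 0.8 and 6.5% at 0.95.

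**The case against.** The strongest reply is that this is one undefined term on a secondary endpoint. The Protocol nowhere states a 48-hour pressure endpoint, MAP and CVP sit in one grouped secondary outcome, and the Publication section calls the physiological findings pilot in nature. Much of this stands: the 48-hour reading is inferred and the consequence is small. It does not remove the conflict, because the hypothesis uses wording that neither its aim nor its outcome shares.

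A reader might draw four stronger conclusions that the Protocol does not support.

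- *That the CVP hypothesis is also set over the whole study period.* It names no window. Only its quantity conflicts with the outcome.
- *That a 48-hour analysis would have almost no power.* The 30% share is not a maximum. Clinicians set each bolus volume, and the treatment-arm volume in 100 mL bottles fills the whole period. Nor does the Protocol show that the effect ends at 4 hours. The Background reports MAP up to four hours after a bolus, which is how long it was followed.
- *That uncontrolled vasopressors hide the effect only in the longer window.* They are uncontrolled in both.
- *That the same data have been shown to confirm and refute the hypothesis.* This is possible with hourly records, but not demonstrated.

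It can also be said that defining *study period*, or adding a 48-hour outcome, would reconcile the text equally well, and that the choice of estimator may be left to an SAP. The first is true. On the second, the Protocol itself fixes relative change as the outcome while stating its CVP hypothesis as a level, so that conflict lies in the Protocol.

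**Conclusion.** The point holds as an inconsistency in the wording of secondary endpoints. For blood pressure, hypothesis and outcome differ in window and quantity, and no listed efficacy outcome tests the hypothesis as worded. For CVP, the hypothesis lacks a window and differs from the outcome in quantity.

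The size of the consequence cannot be derived from the Protocol. Under the assumed 0.30 SD effect confined to post-bolus hours, with equal SDs, power for a 48-hour mean lies between about 15% and 85%, against 85% for the 4-hour window. Free choice between the windows would raise the type I error from 5% to between 6.5% and 9.7% over the assumed correlations. These figures show that the choice of window can matter; the inconsistency does not depend on them.

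The primary outcome, resuscitation fluid over 48 hours, and the sample size are unaffected. This is a minor, inexpensive correction.

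**What to change.** 1. Define *study period* once.
2. Reword the MAP and CVP hypotheses to the 4-hour window of the outcome list, with one start point, for example the first study bolus after randomisation. Use the same window and start in the Aims. The first bolus is preferable to all boluses because the number of later boluses may itself depend on treatment: the Background reports further boluses in 58% of patients on 5% albumin and 45% on 20%.
3. Use one quantity in all three places: mean MAP and mean CVP in mmHg over that window, adjusted for the pre-bolus value, in place of relative change. With that adjustment, the between-arm difference in mean level equals the between-arm difference in absolute change, so one analysis serves both the blood-pressure increase and the CVP level. It also avoids dividing by low baseline CVP values, which the inclusion criteria admit (below 8 mmHg).
4. Report 48-hour mean pressures descriptively, beside vasoactive dose.

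The cost is rewording in the Hypotheses, Aims and Outcome Data. No new data are needed, because pressures are already recorded hourly. The trial gives up a formal 48-hour pressure claim, for which no outcome is listed anyway.
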